## 8. INTRODUCTION

Breast cancer has the highest incidence among cancers in women worldwide [1]. An estimated 2.08 million women worldwide had been diagnosed with breast cancer in 2018, and in a five-year prevalence period, 6.8 million women have breast cancer [1]. In India, the incidence is 162 thousand, with a five-year prevalence is 405 thousand in 2018 [1]. Breast cancer is curable if diagnosed in the early stage. Hence, screening is important for early detection. Mammography is the current gold standard for breast cancer screening. However, mammography is less sensitive on younger women due to denser tissue. Further, the radiation effects due to the X-rays may be harmful enough to cause cancer in younger women [2]. The reported sensitivity of mammography ranges between 64% in extremely dense breast tissue to 90% in less dense tissue [2].

The feasibility of using thermography as an alternative breast imaging modality to current modalities is being evaluated with a goal towards screening of the patients to detect early breast cancer. Niramai has pioneered an advanced method of screening for breast cancer by enhancing thermography with machine intelligence. This combination of thermography and computer aided diagnostics is called Thermalytix™. Patented Niramai's Thermalytix™ solution uses machine learning (advanced data analytics and an upcoming research theme in Computer Science) consisting of probabilistic mathematical modelling of a decision process and statistical analysis of historic data to predict whether the subject belongs to malignant class or benign/normal Class.

#### **RATIONALE FOR STUDY**

The purpose of this study was to evaluate the effectiveness of Thermalytix™ algorithm over popular methods of screening used as the current standard of care.

16 Sep 2020 Confidential Page 19 of 53

## 9. STUDY OBJECTIVES

#### 9.1 PRIMARY OBJECTIVE

- To evaluate the effectiveness of Thermalytix™ for breast cancer screening as compared to standard screening modalities for breast cancer
- 2. To correlate the results of Thermalytix™ with digital mammography for screening diagnostics on patients walking in for health check as measured by:
  - Sensitivity of Thermalytix™ as compared to sensitivity of mammography
  - Specificity of Thermalytix™ as compared to specificity of mammography

#### 9.2 **SECONDARY OBJECTIVES**

- Influence of patient characteristics on diagnostic accuracy of Thermalytix™.
  Patient characteristics will include:
  - Age
  - Lesion type
  - Pathologic diagnosis
  - Menopausal and hormonal status
  - Breast density
  - Family history
- 2. Recommend how Thermalytix™ can be used to complement standard breast cancer screening procedure.

16 Sep 2020 Confidential Page 20 of 53

### 10. INVESTIGATIONAL PLAN

#### 10.1 OVERALL STUDY DESIGN AND PLAN

This was a prospective, comparative study to evaluate the effectiveness of Thermalytix™ when compared to the standard screening modalities in females of age 18 years and above. The study was initiated after appropriate clearance from the ethics committee.

The study visits included a screening visit (Visit 1) followed by visits at Day 2-5 (Visit 2), Day 6-10 (Visit 3) and Day 10-14 (Visit 4):

- 1. The Visit 1 procedures included informed consent process, collection of information regarding current complaints, past medical history and treatment, family history, physical examination, record of risk factors, followed by Thermalytix™ procedures, and mammography as part of routine screening for all woman enrolled in the study. The Mammography machine used was (GE Dmr Plus analog Mammography and Prodigy). Thermalytix employed Algorithm ver 3.0.
- 2. The Visit 2 procedures were based on the results of Thermalytix™ and mammography and were conducted only for the women who had an inconclusive mammography report or who were reported as positive by either or both Thermalytix™ and mammography.
  - If mammography was inconclusive, a confirmatory test which included USG, or MRI scan was recommended by the clinician. The breast ultrasound (USG) was done using Samsung RS85 and MRI was performed on GE 3.0T.
  - If either or both Thermalytix™ and mammography reported the case as positive, a confirmatory test which included USG, MRI, or PET scan was recommended by the clinician. If any of the three tests identified a suspicious lesion, FNAC/biopsy was recommended in the same or follow-up visit.

16 Sep 2020 Confidential Page 21 of 53

- 3. The Visit 3 procedures included FNAC/biopsy and related laboratory work-up. Women underwent MRI guided biopsy in cases where results were positive by MRI.
- 4. The final visit or the Visit 4 was done by telephonic contact and all the procedures were completed for all the subjects enrolled into the study.

Women reported as negative for cancer by both tests (Thermalytix™ and mammography) would complete visits 1 and 4 only. Whereas positive cases and suspected cancer cases completed all visits as applicable. The patients were expected to go through the entire screening process within a duration of 2 weeks from enrollment on the study.

Efforts were made to conclude the screening procedure as early as possible for the subjects. The screening process was completed on the same day when subjects were enrolled in the study. No subject had a screening process that went beyond the allocated time of 14 days.

## 10.2 DISCUSSION OF STUDY DESIGN

The prospective and comparative nature of the study design was the most appropriate approach to evaluate the objectives of the study because the specificity, sensitivity, and accuracy of Thermalytix™ would be beneficial in clinical practice.

This study was done as a comparison to the standard method of mammography. The sensitivity of Thermalytix™ (an automated thermographic screening algorithm developed by Niramai) was compared to the sensitivity of mammography and to study how Thermalytix™ can complement the standard modalities in breast cancer screening in future.

16 Sep 2020 Confidential Page 22 of 53

#### 10.3 **SELECTION OF STUDY POPULATION**

### 10.3.1 Inclusion Criteria

Subjects were eligible for participation in the study if they met the following criteria:

- 1. Female subjects equal to and above 18 years
- 2. Subjects who are willing to give written informed consent for study participation
- 3. Subjects who are ready to comply with the study related visits and procedures

### 10.3.2 Exclusion Criteria

Subjects meeting any of the following criteria will be excluded from the study:

- 1. Subjects who are pregnant
- 2. Subjects who are lactating
- 3. Subjects who have undergone either lumpectomy or mastectomy
- 4. Subjects who have undergone chemotherapy in the last 2 weeks at the time of study enrollment
- 5. Any active illness, psychological and/or pathological condition that would interfere with study participation in the opinion of the Investigator

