## iii. Secondary Effectiveness Analyses

Influence of patient characteristics such as age group, menopause status and breast density on diagnostic accuracy (sensitivity, specificity, PPV and NPV) of Thermalytix™ as compared to that of standard modalities were reported along with 95% confidence interval.

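### Objective 2 concerns health-check attendees, but eligibility is wider and the analysis pools all women, so pooled accuracy cannot be read as screening accuracy until the case mix is shown

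*Combined protocol and SAP*

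**What the plan says.** Section 9.1 sets the second primary objective as a comparison with mammography "for screening diagnostics on patients walking in for health check as measured by" sensitivity and specificity. Section 10.7.2 also counts its sample in screening patients, and section 10.1 describes mammography as routine screening for every enrolled woman.

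Section 10.3.1 has three inclusion criteria: "Female subjects equal to and above 18 years", consent, and readiness to comply. Besides pregnancy and lactation, section 10.3.2 excludes:
- "Subjects who have undergone either lumpectomy or mastectomy";
- "Subjects who have undergone chemotherapy in the last 2 weeks at the time of study enrollment";
- "Any active illness, psychological and/or pathological condition that would interfere with study participation in the opinion of the Investigator".

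Visit 1 (section 10.1) includes "collection of information regarding current complaints, past medical history and treatment". Section 10.7.1 i uses one full analysis set for all analyses, and 10.7.1 ii reports sensitivity, specificity, PPV and NPV with 95% confidence intervals. The secondary analysis in 10.7.1 iii is "Influence of patient characteristics such as age group, menopause status and breast density on diagnostic accuracy". Section 9.2 adds lesion type, pathologic diagnosis, hormonal status and family history as characteristics of interest. Section 10.8.2 reports no change to the analyses.

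**The concern.** The objective names a population, but no eligibility criterion enforces it. Nothing requires a health-check visit or the absence of breast symptoms, and nothing excludes a known cancer that has not been operated on. The chemotherapy exclusion covers only a 2-week window, so a woman treated before that window is eligible. None of the characteristics in 9.2 or 10.7.1 iii separates these women from health-check attendees, although Visit 1 collects information that might.

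Two things are at stake. Sensitivity is an average over cancers, not over women, so a small group with high prevalence can supply most of the cancers and dominate the estimate. PPV and NPV depend directly on prevalence, so pooled values belong to whatever mix was recruited. Section 9.2 intends a recommendation on how the test complements standard screening, and that recommendation needs figures for a screening population.

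**Working it through.** **The plan's own figure.** Section 10.7.2 gives 300 women, 4% prevalence, 80% sensitivity and an exact 95% interval of width 0.487. Cases = 300 × 0.04 = 12, and detected = 0.80 × 12 = 9.6. The Clopper-Pearson limits (Beta quantiles, with the non-integer count kept) are 0.480 and 0.967, width 0.487. This reproduces and is not in dispute. The 4% is a lifetime figure for cancer and other breast abnormalities, so it does not say how many cancers a health-check sample would contain.

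**Predictive values against prevalence.** PPV = Se·p / [Se·p + (1 − Sp)(1 − p)] and NPV = Sp(1 − p) / [Sp(1 − p) + (1 − Se)p]. Sensitivity Se = 0.80 is from 10.7.2. Specificity Sp = 0.90 and the cancer prevalences p are assumed.

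| p | PPV | NPV |
|---|---|---|
| 0.5% | 3.9% | 99.9% |
| 1% | 7.5% | 99.8% |
| 4% | 25.0% | 99.1% |
| 10% | 47.1% | 97.6% |

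**Pooling two groups.** All inputs here are assumed: prevalence 0.5% in health-check women and 10% or 20% in symptomatic women; sensitivity 0.70 and 0.90 respectively; specificity 0.90 in both. Let f be the share of women who are symptomatic and p_s their prevalence.
- Pooled prevalence: p = f·p_s + (1 − f)·0.005
- Share of cancers from symptomatic women: w = f·p_s / p
- Pooled sensitivity: w·0.90 + (1 − w)·0.70

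For f = 10% and p_s = 10%: p = 0.0100 + 0.0045 = 0.0145, w = 0.0100/0.0145 = 0.69, and sensitivity = 0.69 × 0.90 + 0.31 × 0.70 = 0.84.

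| f | p_s | w | Pooled Se | PPV | NPV |
|---|---|---|---|---|---|
| 0 | – | 0 | 0.70 | 3.4% | 99.8% |
| 10% | 10% | 69% | 0.84 | 11.0% | 99.7% |
| 10% | 20% | 82% | 0.86 | 17.8% | 99.6% |
| 25% | 10% | 87% | 0.87 | 20.6% | 99.6% |
| 25% | 20% | 93% | 0.89 | 33.5% | 99.3% |

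If the two groups had equal sensitivity, pooled sensitivity would not move, but PPV still would. In these examples PPV is strongly affected and NPV only slightly. Specificity could also differ between the groups; it is held fixed here.

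**Information in a health-check stratum.** Even if all 459 analysed women belonged to it, assumed prevalences of 0.5% and 1% give 459 × 0.005 = 2.3 and 459 × 0.01 = 4.6 cancers. With 4 of 5 detected, the exact 95% interval is about 28% to 99%, width 0.71, against the target of 0.5 in 10.7.2.

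**The case against.** A reader might infer that the trial's accuracy figures do not describe screening, or that its sensitivity is biased upward. The documents do not support either statement. They contain no accuracy results and no count of symptomatic or previously treated women. Being eligible is not the same as being enrolled, and sections 9.1, 10.1 and 10.7.2 all use the language of a screening setting. If all 459 women were health-check attendees, there is no distortion. That women under cancer treatment entered is only an inference from the 2-week window: the criterion does not name breast cancer, surgically treated women are excluded, and the investigator's discretion may have removed others. Nothing in the documents shows that a cancer already treated with chemotherapy is easier to detect by either test. Both tests are done in the same women, so case mix may shift both sensitivities, and its effect on the comparison is unknown. The available text also passes from 10.4.2 to 10.7, so recruitment source could be described elsewhere.

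All of this stands, and it makes the point conditional. It does not remove it. Describing mammography as routine screening is not an eligibility criterion, and the discretionary exclusion applies only to a condition that would interfere with participation, which a breast symptom need not do.

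The objection to replacing the pooled primary analysis with a health-check stratum also stands: with 2 to 5 cancers, that analysis would say little about sensitivity.

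**Conclusion.** The point holds in conditional form. The objective and the eligibility criteria describe different populations, and no planned analysis separates them. Pooled sensitivity, specificity, PPV and NPV therefore cannot be read as screening accuracy until the case mix is shown. If symptomatic or known-cancer women were enrolled, pooled sensitivity may mainly reflect symptomatic disease, and the predictive values would reflect a higher prevalence than in a health-check population. The size is unknown. The shifts of 14 to 19 points in sensitivity (0.84 or 0.89 against 0.70) and the PPV of 11% to 34% against 3.4% rest wholly on assumed prevalences, sensitivities, specificity and symptomatic shares. They show only that a modest share could matter. The remedy is inexpensive and worth making; an analysis error has not been demonstrated.

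**What to change.** 1. Reconcile the population in objective 2 (section 9.1) with sections 10.3.1 and 10.3.2, and state which women were recruited.
2. In 10.7.1 ii and iii, use the Visit 1 information on complaints, history and treatment to form two groups: women without a breast complaint or breast cancer history or treatment, and the rest.
3. For each group give the number of women, the number of cancers, and sensitivity, specificity, PPV and NPV with exact 95% intervals, for both Thermalytix and mammography.
4. Keep the pooled analysis and set these results beside it, labelled post hoc because the study is complete. Describe PPV and NPV as screening values only for the first group.

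The cost is one stratified table, with no new patients or procedures. The first group may contain few cancers, and its sensitivity interval may be wider than the 0.5 target. The table also depends on the complaint field identifying breast complaints specifically, which the text does not confirm and which should be checked first.

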## 10.3.3 Removal of Subjects from Assessment

Subjects were free to withdraw consent at any time during the study. Data was collected up to the time of withdrawal, but no additional information was collected after this time.

#### 10.4 **STUDY PROCEDURES**

All the enrolled subjects underwent thermal imaging (to conduct Thermalytix™) by a technician trained by the sponsor in strict compliance to the procedure (Appendix I of the

16 Sep 2020 Confidential Page 23 of 53

study protocol) using thermal camera. The thermal images were interpreted by the AI-based algorithm 'Thermalytix™'. The Thermalytix™ report and the standard screening reports were collated by the study coordinator and entered in the CRFs.

The results of Thermalytix™ and mammography were correlated, and the correlation results were analyzed by PI. If the reports of the two tests correlated, a secondary test was not mandated. In case of inconclusive reports from standard modality, subjects underwent confirmatory breast USG/MRI/PET scan as determined by the PI. In case Thermalytix™ identified lesions suspicious of malignancy and mammography did not identify the lesion, to resolve the discrepancy between the two tests, the subject underwent confirmatory breast USG/MRI/PET scan as determined by the PI. USG-guided biopsy was the confirmatory test for cases reported as positive by imaging modalities. MRI-guided biopsy was performed in cases where results were positive for malignancy by MRI. When all the results were received and final diagnosis were confirmed, subjects were contacted telephonically to complete the end of trial procedure and their treatment course was decided by the treating doctor.

Study Coordinator transcribed all the data in the CRF. Data from individual CRFs were entered by the Study Coordinator in the excel spreadsheet and sent to the Data Management group for analysis.

## 10.4.1 Identity of Investigational Product

Thermalytix™: Machine Learning based Automated Thermographic Screening Algorithm 3.0 developed by Niramai.

# **10.4.2** Procedure Compliance

Any non-compliance was reported in CRF as deviation.

16 Sep 2020 Confidential Page 24 of 53

# 10.7 STATISTICAL METHODS PLANNED IN THE PROTOCOL AND DETERMINATION OF THE SAMPLE SIZE

#### 10.7.1 Statistical and Analytical Plans

Analysis of the data was performed by the Biostatistics and Statistical Programming team of Statiza Statistical Services. All statistical analyses were performed using R Software version 3.5.0 and SAS® Version 9.4 or higher [SAS Institute Inc., USA].

The following standard descriptive summaries were presented:

The continuous data was summarized using the number of observations (n), arithmetic mean (mean), standard deviation (SD), median, minimum value (min), and maximum value (max). The categorical variables were summarized using the frequency count (n) and percentage (%) for each possible value. The frequencies were presented up to 0 decimal places and percentage up to 2 decimal places.

Thermalytix™ and standard modalities were evaluated using following measures of validity:

- Sensitivity The probability of correctly identifying a true case of malignancy
- Specificity The probability of correctly identifying a true case of non-malignancy (normal or benign)
- Positive Predictive Value (PPV) The probability that a labelled positive was a true case of malignancy
- Negative Predictive Value (NPV) The probability that a labelled negative was a true case of non-malignancy

All the methods of validity were computed for Thermalytix™ along with their 95% CI.

16 Sep 2020 Confidential Page 29 of 53

## i. Subject Population

FAS Population: All enrolled subjects who underwent thermography (AI-based Thermalytix™) and mammography and satisfied inclusion criteria and rest of the protocol requirement, were considered in Full Analysis set (FAS). All statistical analyses were performed considering FAS population.

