## ii. Primary Effectiveness Analysis

Sensitivity, specificity, PPV and NPV of Thermalytix™ as compared to that of standard modalities were reported along with 95% confidence interval.

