# 10.7.2 Determination of Sample Size

The sample size was calculated with two-sided 95% confidence interval (CI) for a sample sensitivity and target width of 0.5 using Clopper-Pearson Interval (Exact) Method. The prevalence of breast cancer and other breast abnormalities in Indian women during their lifetime was assumed to be 4% (1 in 25 were expected to have a breast abnormality in their lifetime in India). A sample size of 300 screening patients allows estimating the true prevalence by means of an exact 95% confidence interval with width of 0.487 percent points when the sample sensitivity was assumed to be 80%. Considering exclusions from data analysis due to multiple visits needed, over 600 women were recruited. Eventually, data of 459 women could be used for statistical analysis as they satisfied inclusion criteria and adhered to the study protocol.

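### The only analysis set is called a Full Analysis Set but is in effect per-protocol, and exclusion for incomplete work-up would depend on the results of the tests being compared

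*Combined protocol and SAP*

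**What the plan says.** Section 10.7.1, i. Subject Population, sets three conditions for the analysis set. A woman must have had both thermography and mammography, and she must have "satisfied inclusion criteria and rest of the protocol requirement, were considered in Full Analysis set (FAS". The same paragraph adds: "All statistical analyses were performed considering FAS population". The supplied text names no other set.

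Section 10.7.2 gives the counts. On recruitment: "Considering exclusions from data analysis due to multiple visits needed, over 600 women were recruited". On analysis: "data of 459 women could be used for statistical analysis as they satisfied inclusion criteria and adhered to the study protocol".

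Section 10.1 sets the visit schedule. Both tests are done at Visit 1 for every enrolled woman. Visit 2 (further imaging) is held only if either test is positive or the mammogram is inconclusive, and Visit 3 covers FNAC or biopsy. Women negative on both tests have only Visit 1 and the Visit 4 telephone contact. Section 10.1 also states that every enrolled woman completed all procedures and that nobody's screening ran past 14 days.

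The comparison at stake is primary. Section 9.1 lists sensitivity, and the specificity of Thermalytix "as compared to specificity of mammography". The primary analysis reports accuracy "as compared to that of standard modalities were reported along with 95% confidence interval".

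**The concern.** A full analysis set normally keeps eligible women whether or not they later followed the protocol. Here later adherence is a condition of entry, and section 10.7.2 confirms that adherence was applied to the 459.

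In this design the label matters because the protocol asks more of some women than of others, and the results of the two tests decide which. A flagged woman (positive on either test, or inconclusive on mammography) must return for imaging and perhaps biopsy. A double-negative woman needs only a telephone call after Visit 1. If failure to complete work-up removes a woman, removal depends on the results being evaluated. False positives can then leave the set while double-negative women stay, and both specificities rise. With a single per-protocol set and no second analysis, a reader cannot tell whether this happened.

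**Working it through.** **1. The plan's own figures.** The width in section 10.7.2 reproduces. With 300 × 0.04 = 12 cases and 0.8 × 12 = 9.6 detected, the exact 95% interval runs from 0.4796 to 0.9670, a width of 0.487. Since 459 exceeds the planned 300, the question is selection, not precision.

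**2. Women not analysed.** 600 − 459 = 141, and 141/600 = 23.5%. Because recruitment was over 600, this is a lower bound.

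**3. What the 141 can contain.** Any of the following would put a woman outside the 459: not meeting the eligibility criteria; lacking one of the tests; being recruited but not enrolled (10.7.1 counts from enrolled women, 10.7.2 from recruited women); missing the Visit 4 call; or not completing Visits 2–3. Only the last is tied directly to the test results. The supplied text gives no split.

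**4. Size under assumed values.** None of the accuracy figures for specificity is in the documents. Assume 600 women, 4% cancers, specificity 80% for Thermalytix (T) and 90% for mammography (M, inconclusive counted as positive), sensitivity 80% for both, and independent results given disease status. The 4% is borrowed from section 10.7.2, where it is a lifetime figure that includes other abnormalities. Expected counts:

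| | T+M+ | T+M− | T−M+ | T−M− |
|---|---|---|---|---|
| No cancer (576) | 11.52 | 103.68 | 46.08 | 414.72 |
| Cancer (24) | 15.36 | 3.84 | 3.84 | 0.96 |

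The 0.96 unverified cancers are left out of the formulas; counting them as non-malignant moves specificity by under 0.1 point. Let *a* be the fraction lost among flagged women and *b* the fraction lost among double-negative women.

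- Denominator: 414.72(1−b) + 161.28(1−a)
- T specificity: [414.72(1−b) + 46.08(1−a)] / denominator
- M specificity: [414.72(1−b) + 103.68(1−a)] / denominator

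For a = 0.25 and b = 0: T = 449.28/535.68 = 83.9%, M = 492.48/535.68 = 91.9%. For a = 0.25 and b = 0.10: T = 407.81/494.21 = 82.5%, M = 451.01/494.21 = 91.3%.

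Sensitivity is taken among verified cancers: 19.2/23.04 = 83.3% for each test before any loss.

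| Loss | T spec. | M spec. | Gap (points) | T sens. | M sens. |
|---|---|---|---|---|---|
| None, or equal in all women | 80.0% | 90.0% | 10.0 | 83.3% | 83.3% |
| 25% of flagged | 83.9% | 91.9% | 8.1 | 83.3% | 83.3% |
| 25% of flagged, 10% of double-negative | 82.5% | 91.3% | 8.7 | 83.3% | 83.3% |
| 50% of T+M− only | 87.9% | 89.0% | 1.1 | 81.8% | 90.9% |
| 50% of T−M+ only | 79.2% | 93.8% | 14.6 | 90.9% | 81.8% |
| 50% of T+M+ only | 80.8% | 90.9% | 10.1 | 75.0% | 75.0% |

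The second row loses 0.25 × 184.32 = 46 women, well within the 141.

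**5. Dependence on inputs (25% of flagged lost).** With M specificity 95% the gap goes from 15.0 to 12.0. With T specificity 70% it goes from 20.0 to 16.5. With both at 90% it stays 0, but each rises to 92.1%. A 1% cancer rate gives the same specificities.

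**6. Bounds for the 46 lost women.** They split as T+M+ 6.72, T+M− 26.88, T−M+ 12.48.

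- All non-malignant: T = (449.28 + 12.48)/581.76 = 79.4%, M = (492.48 + 26.88)/581.76 = 89.3%, gap 9.9.
- All malignant: specificities stay at 83.9% and 91.9%. Sensitivities become 48.0/63.36 = 75.8% and 33.6/63.36 = 53.0%, with 63.36/600 = 10.6% of women malignant.

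**The case against.** The strongest reply is that the documents partly contradict the mechanism. Section 10.1 says all procedures were completed for all enrolled women and that no one exceeded 14 days. Read literally, this argues against incomplete work-up. It stands as a reason not to claim bias. It leaves open why 141 or more women are missing, so the statements need reconciling.

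A reader might infer that nearly a quarter of the women were dropped for unfinished work-up and that specificity is therefore inflated. The documents do not support this. The expected multiple-visit exclusions explain why more women were recruited; they do not say why these particular women were left out. Ineligible women and women without both tests would be outside any reasonable set. The supplied text also passes from section 10.4.2 to 10.7, with page footers going from 24 to 29, so a disposition account may exist elsewhere and its absence here is no fault.

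A reader might also suspect the third inclusion criterion, "Subjects who are ready to comply with the study related visits and procedures", of acting as a filter applied after the results. It describes readiness at entry, and nothing says it was judged later.

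Finally, double-negative women also have a second contact at Visit 4 and can be lost too. That is right, and it shrinks the effect: 8.7 points rather than 8.1 in the table above.

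**Conclusion.** The point holds in a limited form. The single set is mislabelled: by its wording and by section 10.7.2 it is per-protocol. At least 141 of over 600 recruited women are not analysed, and the share removed by the adherence condition is unknown. Any exclusion for incomplete work-up would depend on the test results and can move the primary comparison. Under the assumed values, 25% loss confined to flagged women adds 3.9 points to Thermalytix specificity and takes 1.9 points off the gap. Loss confined to one test pattern moves sensitivity as well as specificity, in either direction. Equal loss in all women does nothing. These sizes rest on assumed accuracy and independent results. Bias is possible, not shown, and the change below is a cheap improvement. Double-negative women without a reference test are a separate matter.

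**What to change.** 1. Relabel the 459-woman set as per-protocol. Beside it, report both tests' accuracy in a supplementary set: all enrolled, eligible women with a Thermalytix result and a mammogram report (including inconclusive), whether or not work-up was completed. Section 10.8.2 refers to a database lock already passed, so an added set is preferable to replacing the main one after the data are known.
2. In the supplementary set, give the complete-case estimate as the point estimate. Add bounds with unverified flagged women taken as all non-malignant, then all malignant. The first is the informative bound for specificity, since the second returns the complete-case specificity. The all-malignant bound is a limit only.
3. Tabulate exclusions by reason and by Thermalytix × mammography result, unless this is already reported in sections not supplied.
4. Reconcile the section 10.1 statements on completed procedures and the 14-day limit with the counts in section 10.7.2, including whether recruited and enrolled mean the same.

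The cost is SAP wording and some reanalysis, feasible only where both Visit 1 results exist. Both tests belong to Visit 1, and section 10.3.3 states: "Data was collected up to the time of withdrawal, but no additional information was collected after this time". Women who left after Visit 1 should therefore have both results, but this needs checking. The downside is wider or less favourable estimates.
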